Official Title: Management of Spontaneous Ruptured Hepatocellular Carcinoma

- Partial Hepatectomy and Prognosis: A Retrospective Study

NCT number: Not available

Date of the document: 05/03/2018

Statistical analysis plan

All of the analyses were carried out using SPSS 24.0 (IBM), and a two-sided $P < 0.05$ was considered statistically significant.

1. A comparison of the clinicopathologic characteristics of all the patients between the partial hepatectomy group and the non-surgical treatment group before propensity score matching (PSM): there are (or no) significances for patients' characteristics before PSM.

The variables are: age, sex, HBs-Ag (+), HCV-Ab, tumor size, tumor number, macroscopic vascular invasion (MVI), cirrhosis, portal hypertension, Child-Pugh grade, hemorrhagic shock, hemoglobin, red blood cell (RBC), transfusion during hospitalization, a-fetoprotein (AFP), aspartate aminotransferase (AST), albumin, total bilirubin, Barcelona Clinic Liver Cancer (BCLC) stage, sorafenib, 30-day mortality.

Statistical analysis method: Pearson's χ^2 test, χ^2 test with Yates' correction, Fisher's exact test, Wilcoxon's rank-sum test and Student's t test.

2. Univariate and multivariate analysis of the predictive factors associated with overall survival (OS) before PSM: surgery or non-surgical treatment is (or not) an independent risk factor of overall survival.

The variables included are: age, sex, tumor size, tumor number, MVI, cirrhosis, portal hypertension, treatment, hemorrhagic shock, distant metastasis, AST, AFP, platelet, hemoglobin, sorafenib, Child-Pugh grade.

Statistical analysis method: univariate analysis was performed using the Kaplan-Meier method compared by the log-rank test; multivariate analysis was performed using the COX regression model.

3. A comparison of the clinicopathologic characteristics of all of the patients between the partial hepatectomy group and the non-surgical treatment group after PSM: there is no significance for patients' characteristics after PSM.

The variables included in PSM are: age, sex, tumor size, tumor number, MVI, cirrhosis, portal hypertension, hemorrhagic shock, hemoglobin, red blood cell (RBC), transfusion during hospitalization, a-fetoprotein (AFP), aspartate aminotransferase (AST), albumin, total bilirubin.

Statistical analysis method: PSM, a caliper of 0.5, 0.3, 0.2, 0.1, 0.05, 0.02, 0.01 would be used.

4. Univariate and multivariate analysis of the predictive factors associated with OS after PSM: surgery or non-surgical treatment is (or not) an independent risk factor of overall survival.

The variables included are: age, sex, tumor size, tumor number, MVI, cirrhosis, portal hypertension, treatment, hemorrhagic shock, distant metastasis, AST, AFP, platelet, hemoglobin, Sorafenib, Child-Pugh grade.

Statistical analysis method: univariate analysis was performed using the Kaplan-Meier method compared by the log-rank test; multivariate analysis was performed using the

COX regression model.

5. Comparison of OS and recurrence-free survival (RFS) between the emergency partial hepatectomy group and the staged partial hepatectomy group.

Statistical analysis method: univariate analysis was performed using the Kaplan-Meier method compared by the log-rank test.

6. Comparison of OS and RFS between the staged early partial hepatectomy group and the staged late partial hepatectomy group.

Statistical analysis method: univariate analysis was performed using the Kaplan-Meier method compared by the log-rank test.

7. Difference in 30-day mortality of peritoneal dissemination between the groups at different times.

Statistical analysis method: Pearson's χ^2 test, χ^2 test with Yates' correction and Fisher's exact test.

8. Univariate and multivariate logistic regression analysis of postoperative peritoneal dissemination.

The variables included are: age, sex, tumor size, tumor number, MVI, cirrhosis, estimated intraperitoneal bleeding, Child-Pugh grade, tumor differentiation, resection margin, type of hepatectomy, timing of hepatectomy.

Statistical analysis method: univariate and multivariate logistic regression analysis.

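### Item 3 matches on transfusion over the whole hospital stay, which can be a consequence of the treatment being compared

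*SAP*

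**What the plan says.** SAP item 3 fixes the covariates of the propensity score, opening with "The variables included in PSM are: age, sex, tumor size, tumor number, MVI, cirrhosis, portal hypertension" and closing with "transfusion during hospitalization, a-fetoprotein (AFP), aspartate aminotransferase (AST), albumin, total bilirubin". Shock and hemoglobin are also in the list. The patients matched are the two treatment groups, whose characteristics are then compared "between the partial hepatectomy group and the non-surgical treatment group after PSM". On the match itself, the item says that "a caliper of 0.5, 0.3, 0.2, 0.1, 0.05, 0.02, 0.01 would be used", without giving the scale.

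Item 4 analyses the matched sample for "predictive factors associated with OS after PSM: surgery or non-surgical treatment is (or not) an independent risk factor of overall survival". Its Cox list contains shock and hemoglobin but not transfusion.

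The surgical group is not uniform in timing. Item 5 compares survival "between the emergency partial hepatectomy group and the staged partial hepatectomy group", and item 6 "between the staged early partial hepatectomy group and the staged late partial hepatectomy group". The SAP does not say which of these operations took place in the stay over which transfusion is counted.

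**The concern.** A propensity score should use information that exists before treatment. Transfusion is the only variable in the item 3 list whose label carries a time window, and that window runs past the treatment decision. Emergency hepatectomy, at least, can be expected to fall inside it.

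Transfusion then has two sources: the bleed, which marks severity before treatment, and the treatment itself. If treatment shifts the second source, the same transfusion status means a different average severity in each arm. Balancing on it unbalances severity. The item 3 comparison after matching would not show this, because transfusion itself would look balanced. The problem reaches overall survival through the choice of matched patients, and item 4 can correct it only as far as shock and hemoglobin capture bleeding severity.

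At stake is the item 4 conclusion on whether surgery is an independent factor for overall survival.

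**Working it through.** The SAP states no sample size, event count, transfusion rate or effect size, so there is no figure to reproduce. The wording settles whether the window is wrong. The calculations below only show direction and a plausible order of size, and every input to them is assumed.

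**Step 1. Mechanism by hand.** Assume 40% of patients bleed severely, equally in both arms, and that the probability of pre-treatment transfusion is 0.15 + 0.45 × severe, i.e. 0.15 or 0.60. Read the effect of surgery as adding 0.20 or 0.40 to those probabilities.

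| Group | Transfused | Severe among transfused | Severe among untransfused |
|---|---|---|---|
| Non-surgical | 0.4×0.60 + 0.6×0.15 = 0.33 | 0.24/0.33 = 73% | 0.16/0.67 = 24% |
| Surgical, +20 points | 0.4×0.80 + 0.6×0.35 = 0.53 | 0.32/0.53 = 60% | 0.08/0.47 = 17% |
| Surgical, +40 points | 0.4×1.00 + 0.6×0.55 = 0.73 | 0.40/0.73 = 55% | 0/0.27 = 0% |

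With equal arms matched 1:1 on transfusion alone, the matched fraction is the smaller of the two shares in each transfusion class.

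- +20: 0.33 transfused and 0.47 untransfused. Severe bleeding is (0.33×0.604 + 0.47×0.170)/0.80 = 35% in the surgical arm and (0.33×0.727 + 0.47×0.239)/0.80 = 44% in the non-surgical arm.
- +40: 0.33 and 0.27. Severe bleeding is (0.33×0.548 + 0.27×0)/0.60 = 30% against (0.33×0.727 + 0.27×0.239)/0.60 = 51%.

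The arms were equal at 40% before matching, so the match created the difference. At +40 it also keeps only 60% of possible pairs.

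**Step 2. Simulation with shock and hemoglobin in the score.** Inputs as in step 1, plus:

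- severe-bleed HR of 2 or 3;
- shock sensitivity/specificity 0.6/0.90 with hemoglobin 1.0 SD lower if severe, or 0.8/0.95 with 1.5 SD;
- median survival 12 months, censoring at 60;
- 1:1 greedy nearest-neighbour matching without replacement, all seven calipers, on the probability scale and in SD of the logit;
- arms 30:70, 50:50 and 70:30;
- Cox model with treatment, shock and hemoglobin;
- N = 100,000 per setting, Monte Carlo error of one HR about 0.01.

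True HR 1, calipers 0.01 to 0.05:

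| Effect of treatment on transfusion | Severe bleeding after matching, surgical vs non-surgical (median) | HR range (median) |
|---|---|---|
| None | – | 0.99-1.01 |
| Surgery +20 | 37-38% vs 42% | 0.94-0.99 (0.97) |
| Surgery +40 | 35-36% vs 45% | 0.88-0.96 (0.93) |
| Non-surgical +20 | 42% vs 38% | 1.02-1.06 (1.04) |
| Non-surgical +40 | 45% vs 35% | 1.04-1.15 (1.09) |
| Pre-treatment window used instead | – | 0.98-1.02 |

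Shock and hemoglobin shrink the imbalance of step 1 but do not remove it. As a rough check, the ratio of average starting hazards is [1 + (h−1)p₁]/[1 + (h−1)p₀], where h is the severe-bleed HR and p₁, p₀ are the severe fractions in the surgical and non-surgical arms. At +40, with p₁ = 0.355 and p₀ = 0.45, it is 1.355/1.45 = 0.93 for h = 2 and 1.71/1.90 = 0.90 for h = 3, in line with the table.

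**Step 3. Sensitivity.**

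- Half of the operations in the stay: 0.97-1.00 (+20) and 0.94-1.00 (+40). A quarter: 0.99-1.01 and 0.97-1.00.
- Caliper 0.5: the bias vanishes (0.99-1.01) only with equal arms and a probability-scale caliper. With 30:70 or 70:30 arms it stays at 0.94-0.98 (surgery +20) and 0.89-0.96 (surgery +40).
- A separate simulation with fine score strata and other assumed inputs, true HR 1.00: 1.00 with pre-treatment transfusion in the score, 0.89 with whole-stay transfusion if surgery raises it, 1.11 if surgery lowers it.

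**Step 4. Confounded treatment choice.** In 32 settings (N = 150,000, caliper 0.02 SD of the logit), severe bleeders were operated on in 35% and others in 60%, or the reverse. Against the pre-treatment window, the whole-stay window moved the HR by 0.01-0.06 (+20) and 0.02-0.15 (+40). It was further from 1 in 16 settings and closer in the other 16. The pre-treatment window itself left 0.89-0.96 or 1.05-1.14.

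**The case against.** The strongest reply is that harm needs two things the SAP does not report: operations in the stay over which transfusion is counted, and treatment that changes transfusion. If most staged operations fell in a later admission, transfusion in the first stay precedes treatment for those patients. With a quarter of operations in the stay, the shift is close to Monte Carlo error. The largest values need a 40-point effect, and for surgery also every operation in the stay. This stands as a limit on size; it does not make the window right.

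Second, the shift may be small beside sampling error. If the matched set had 100 to 300 deaths (an assumption) in equal arms, the SE of the log HR, 2/√deaths, would be 0.20 to 0.12. The median shift for surgery +20 (ln 0.97 = −0.03) is then about 0.15 to 0.26 SE, and for +40 (ln 0.93 = −0.07) about 0.36 to 0.63 SE. This also stands, though a larger sample would not remove the bias.

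Third, treatment choice in a retrospective series is probably confounded, and there the pre-treatment window was not uniformly closer to the truth. That is correct. The offset in half of the settings came by chance from the chosen directions and cannot be relied on. The case for the change rests on not conditioning on a post-treatment variable, not on a proven gain in this study.

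Fourth, a protocol or chart-abstraction form not shown might restrict the variable to preoperative blood. If so, one phrase closes the point. The SAP, however, does not leave the window open; it states one.

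Finally, the comma between the red-cell and transfusion entries may be stray, so that one variable is meant. The point holds on either reading.

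**Conclusion.** The concern holds. As written, item 3 can put a consequence of treatment into the propensity score, and item 4 draws its survival conclusion from the resulting match. The bias favours surgery if surgery raises transfusion over the stay, goes against surgery if non-surgical patients receive more, and is about zero if treatment does not change transfusion. Neither direction nor size can be determined from the SAP. On the assumed inputs, the median shift was 0.03 to 0.04 on the HR for a 20-point effect and 0.07 to 0.09 for a 40-point effect, less if fewer operations fall in the stay. These are illustrations, not estimates for this study. The change should be made, on grounds of principle and low cost; confidence is medium because of the unknowns above.

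**What to change.** In item 3, redefine the variable as transfusion before the operation or treatment decision, with a comparable time point for non-surgical patients, using dates from the same charts. The cut-off must apply to both arms: shortening only the surgical window while counting the whole stay for non-surgical patients recreates the bias in the opposite direction. State at the same time whether the red-cell entry and the transfusion entry are one variable or two.

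If dates cannot be recovered, omit the variable from the main score and report the match and the item 4 result with and without it.

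The cost is a change of wording plus chart work to date transfusions, which may not be feasible for every patient. Omission loses one severity marker, although shock and hemoglobin remain: in the confounded runs the HR was then 0.00-0.03 further from 1 than with the pre-treatment window. Neither option removes residual confounding by bleeding severity.

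### 30-day mortality, an outcome, is listed as a patient characteristic in SAP item 1, so its only specified surgery versus non-surgery test is unadjusted and made before matching

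*SAP*

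**What the plan says.** Item 1 of the SAP compares clinicopathologic characteristics between the partial hepatectomy and non-surgical groups before PSM. The last three entries in its list are "Barcelona Clinic Liver Cancer (BCLC) stage, sorafenib, 30-day mortality". The methods are "Pearson's χ^2 test, χ^2 test with Yates' correction, Fisher's exact test, Wilcoxon's rank-sum test and Student's t test", all unadjusted two-group tests, and the result is left open: "there are (or no) significances for patients' characteristics before PSM". The general rule is that "a two-sided $P < 0.05$ was considered statistically significant".

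Item 3 repeats the comparison after PSM and states its result in advance: "there is no significance for patients' characteristics after PSM". The only list it prints is introduced as the matching variables: "The variables included in PSM are: age, sex, tumor size, tumor number, MVI, cirrhosis, portal hypertension, hemorrhagic shock" and so on. 30-day mortality is not in that list.

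The matched treatment comparison of an outcome is item 4, "Univariate and multivariate analysis of the predictive factors associated with OS after PSM", by log-rank test and Cox regression. Item 2 does the same before PSM. 30-day mortality is named once more, in item 7: "Difference in 30-day mortality of peritoneal dissemination between the groups at different times".

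**The concern.** A table of characteristics describes who was treated. 30-day mortality describes what happened afterwards. Classing it with age and tumor size has a practical effect: it receives the tests meant for describing the unmatched groups and none of the adjustment that the plan gives its survival outcome.

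The plan uses PSM because it expects operated and non-operated patients to differ. Shock, bleeding and liver function plausibly influence both the choice of surgery and death within a month. A crude 30-day comparison is therefore highly exposed to the selection that PSM is meant to reduce. A reader of the results table would see a P value for early death by treatment with no matched counterpart.

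The secondary issue is the scope of item 3. If its statement of no significance covered everything in item 1's table, an outcome would be judged by a standard meant for covariate balance.

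**Working it through.** **Where 30-day mortality appears.** This is a check of the text; the SAP gives no figure to reproduce.

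| SAP item | Groups compared | Role of 30-day mortality | Adjusted or matched? |
|---|---|---|---|
| 1 | surgery vs non-surgery, before PSM | listed as a characteristic | no |
| 2 | surgery vs non-surgery, before PSM, OS | not named | OS adjusted by Cox |
| 3 | surgery vs non-surgery, after PSM | not in the printed list | scope unclear |
| 4 | surgery vs non-surgery, after PSM, OS | not named | OS matched and adjusted |
| 7 | groups at different times | named, tied to peritoneal dissemination | no, and a different contrast |

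Items 5, 6 and 8 do not name it. Item 1 is thus the only place that explicitly specifies a surgery versus non-surgery test of it.

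**Item 1 against item 3.** As punctuated, item 1 lists 21 variables and item 3 lists 15, all of which are in item 1. The 21 − 15 = 6 left out are HBs-Ag, HCV-Ab, Child-Pugh grade, BCLC stage, sorafenib and 30-day mortality. Two readings of item 3 follow:

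- *Narrow:* only the 15 matching variables are compared after PSM. 30-day mortality is then tested only before matching, and nothing is said about its matched result.
- *Broad:* item 1's table is repeated after PSM. 30-day mortality is then tested in the matched set as well, but under a heading that states no significance in advance.

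The two cannot both apply, and the text does not choose. Under neither is 30-day mortality specified as an outcome with a matched effect estimate.

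**Illustration of crude bias (assumed inputs).** For a single binary confounder with the same effect on risk in both groups and no treatment effect:

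crude risk difference = (difference in confounder prevalence, surgery minus non-surgery) × (difference in 30-day mortality with and without the confounder).

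Simulations with no true effect, 300 to 500 patients, six confounders and non-surgical mortality of about 25 to 30% gave crude differences of about −8 to −10 points, and about 0 after matching at a caliper of 0.2. By the formula, one confounder gives the same if prevalence differs by 0.20 and mortality by 0.40 (−0.20 × 0.40 = −0.08), or by 0.25 and 0.40 (−0.25 × 0.40 = −0.10). With no confounding it is 0.

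The chance that such a spurious difference reaches two-sided P < 0.05 follows from a normal approximation. Assume equal groups of n/2 and non-surgical mortality of 28%, with SE = √[(p₀(1−p₀) + p₁(1−p₁)) / (n/2)]:

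| Spurious difference | n | SE | z = difference/SE | chance of P < 0.05 |
|---|---|---|---|---|
| 8 points (28% vs 20%) | 300 | 0.0491 | 1.63 | 37% |
| 8 points | 500 | 0.0380 | 2.10 | 56% |
| 10 points (28% vs 18%) | 300 | 0.0482 | 2.07 | 55% |
| 10 points | 500 | 0.0374 | 2.68 | 76% |

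The nominal rate is 5%. None of these inputs comes from the SAP. The strength of confounding, which drives the result, is a free choice.

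**The case against.** The strongest defence is that OS is the outcome the plan ties to treatment. Item 1 draws a conclusion only about characteristics, and the SAP states no early-mortality hypothesis for surgery versus non-surgery. Deaths within 30 days are also OS events, and items 2 and 4 analyse OS by treatment with adjustment, item 4 after matching as well. This stands in part: it would be wrong to say that early deaths are only ever handled crudely. But a log-rank test or a single hazard ratio over all follow-up does not isolate the first 30 days, where operative risk may differ from the later effect. Matched Kaplan-Meier curves could be read at day 30, but the SAP does not specify that estimate.

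A reader might infer that item 3 requires 30-day mortality to be non-significant after matching. The text does not say so: the list nearest to that statement is the matching list, which omits it. A reader might go further and infer that the caliper would be tightened until mortality is non-significant, so that a real effect is hidden. Item 3 says only that seven calipers would be used. It states no rule for tightening or choosing among them, and reporting all seven is an equally available reading. Any power loss computed for such a rule would describe a rule that the plan does not contain.

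Sorafenib is in the same list, but the SAP does not say when it was started, so the same charge cannot be made against it. Finally, matching as planned is no guarantee of an unbiased result. Child-Pugh grade, for example, is not a matching variable, although albumin and bilirubin are. The zero bias after matching in the illustration assumes that every relevant confounder was matched.

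**Conclusion.** The point holds in limited form. An outcome is classed as a characteristic, and the only explicitly specified surgery versus non-surgery test of it is unadjusted and in the unmatched groups. This rests on the SAP's own lists and needs no assumption. The scope of item 3 is a secondary ambiguity, not a demonstrated error.

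The size of the bias cannot be established from the document. The 8 to 10 points illustrate moderately strong confounding; the true figure could be near zero or larger. The direction also depends on which patients were selected for surgery. The OS conclusions of items 2 and 4 are not affected. The change should be made because it removes an avoidable source of bias from a reported comparison at little cost.

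**What to change.** 1. Remove 30-day mortality from the characteristics in item 1.
2. In item 3, list the variables compared after matching. State that the balance check covers only variables known before treatment and never 30-day mortality. For entries whose timing is not given, such as sorafenib and transfusion during hospitalization, say whether they precede treatment.
3. Add 30-day mortality to item 4 as an outcome in the matched set, reported as a risk difference with 95% CI by a method that respects the matching. If matching is 1:1, a paired risk difference with McNemar's test serves; the SAP does not state the ratio, so the method should follow from it.

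The cost is a few lines of wording and one extra analysis of data already collected. The downside is lower precision: the matched set is smaller than the full cohort, so the interval will be wider than the crude one.

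### SAP items 2 and 4 enter sorafenib as a fixed factor in the overall survival models; if it starts after time zero, its own hazard ratio is biased towards benefit and the surgery hazard ratio can be biased too.

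*SAP*

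**What the plan says.** Item 2 (before propensity score matching, PSM) lists the OS factors, with treatment among them and ending "hemorrhagic shock, distant metastasis, AST, AFP, platelet, hemoglobin, sorafenib, Child-Pugh grade". Item 4 repeats the list after PSM: "hemorrhagic shock, distant metastasis, AST, AFP, platelet, hemoglobin, Sorafenib, Child-Pugh grade". Both items give the same methods: "univariate analysis was performed using the Kaplan-Meier method compared by the log-rank test", and "multivariate analysis was performed using the COX regression model". Both state the same target: whether "surgery or non-surgical treatment is (or not) an independent risk factor of overall survival". The test level is "a two-sided $P < 0.05$ was considered statistically significant".

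Item 1 lists sorafenib among the characteristics compared between groups, in the run "Barcelona Clinic Liver Cancer (BCLC) stage, sorafenib, 30-day mortality". The PSM variable list in item 3 does not contain sorafenib.

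Nowhere does the SAP give a start date, a landmark, a time-dependent term or a definition of the sorafenib variable.

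**The concern.** Kaplan-Meier curves compared by log-rank need groups that are fixed at time zero, and a Cox model with no further specification treats each covariate as known then. Sorafenib coded as ever or never used meets that requirement only if use was already settled at time zero. If it begins later, two problems follow.

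- **Immortal time.** A patient must survive to the start date to be classed as a user. Those who die first are counted as non-users. The sorafenib HR then falls below its true value in the log-rank comparison and in the Cox model, whatever the balance of use between groups.
- **Adjustment for a later event.** If use differs between the surgical and non-surgical groups, the distorted sorafenib term carries part of the survival difference and shifts the surgery HR. Separately, if the drug does affect survival and its use follows from the index treatment, adjusting for it replaces the total effect of surgery with an effect conditional on later therapy.

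Matching on the item 3 variables cannot be relied on to remove either problem. The main conclusion of items 2 and 4 is read from these models.

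**Working it through.** The SAP gives no sample size, event count, effect size, sorafenib use by group or start time, so there is no figure of its own to reproduce. All inputs below except the model forms are assumptions.

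**1. Why a null drug looks protective.** Let OS be exponential with hazard h = ln 2 / (median OS), and let time to sorafenib start among intended users be exponential with rate λ = ln 2 / (median start). Ignoring the follow-up limit, the share of intended users who live to start is

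λ/(λ + h) = median OS / (median OS + median start).

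With median OS 6 months and 30% intended users, the share classed as users is:
- median start 1 month: 0.30 × 6/7 = 0.26
- median start 3 months: 0.30 × 6/9 = 0.20
- median start 6 months: 0.30 × 6/12 = 0.15

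At 6 months, half the intended users die first and count as non-users. Mean OS of those classed as users is 1/(λ + h) + 1/h = 4.3 + 8.7 = 13.0 months, against 8.7 months for everyone, with a drug that does nothing.

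**2. Size when only a subset is ever going to start.** Simulation: 200,000 patients per scenario, groups 1:1, exponential OS, non-surgical median 6 months, censoring at 60 months, true sorafenib HR 1.0. Use is the intended share, surgical/non-surgical. The three values in a cell are for a median start of 1, 3 and 6 months.

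| True surgery HR | Use | Sorafenib HR, fixed | Surgery HR, fixed |
|---|---|---|---|
| 1.0 | 30/30% | 0.83, 0.68, 0.61 | 1.01, 0.99, 0.99 |
| 1.0 | 50/10% | 0.80, 0.64, 0.57 | 1.10, 1.16, 1.15 |
| 1.0 | 10/50% | 0.80, 0.65, 0.57 | 0.92, 0.87, 0.86 |
| 0.7 | 50/10% | 0.83, 0.67, 0.58 | 0.75, 0.80, 0.82 |
| 0.7 | 10/50% | 0.81, 0.66, 0.58 | 0.64, 0.61, 0.61 |
| 0.5 | 30/30% | 0.86, 0.73, 0.64 | 0.50, 0.50, 0.51 |
| 0.5 | 50/10% | 0.87, 0.73, 0.62 | 0.53, 0.56, 0.58 |
| 0.5 | 10/50% | 0.81, 0.66, 0.59 | 0.46, 0.44, 0.43 |

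- Over all scenarios run, the fixed sorafenib HR was 0.57 to 0.89. A repeat run reached 0.92 at the upper end.
- The largest surgery shift in the table is 0.82/0.70 = 1.17, or 17%. The repeat run reached about 18%.
- With use of 30/10% or 10/30%, the surgery shift was about 2 to 7%.
- With sorafenib starting at time zero, neither HR was materially biased.
- Time-dependent coding gave a sorafenib HR of 0.98 to 1.02 and surgery HRs within 0.01 of the truth. Omitting sorafenib also recovered the surgery HR, because the simulated drug has no effect.

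**3. Size when every survivor stays at risk of starting.** Simulation: 8,000 patients per scenario, non-surgical median OS 8 months, 60 months of follow-up, null drug. The sorafenib HR was about 0.37 to 0.44. Shares are observed use, surgical against non-surgical.

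| True surgery HR | Observed use | Surgery HR, fixed | Shift |
|---|---|---|---|
| 1.0 | 10% v 31% | 0.77 | −23% |
| 1.0 | 6% v 26% | 0.78 | −22% |
| 1.0 | 25% v 10% | 1.21 | +21% |
| 1.0 | 18% v 18% | 0.98 | −2% |
| 0.5 | 18% v 32% | 0.37 | 0.37/0.50 = 0.74, −26% |
| 0.5 | 41% v 10% | 0.68 | 0.68/0.50 = 1.36, +36% |

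The formula in step 1 shows how extreme this set-up is. Observed shares of 10% and 31% at a median OS of 8 months need median starts of about 72 and 18 months, since 8/80 = 0.10 and 8/26 = 0.31. Keeping those observed shares but letting only a subset start at a median of 1, 3 or 6 months cuts the 23% shift to about 3%, 8% or 13%. For 25% against 10%, the 21% shift becomes about 2%, 6% or 8%.

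**The case against.** The strongest reply is that the SAP never says sorafenib starts after the index treatment. A reader might infer a later start from its absence from the PSM list, but that list also omits Child-Pugh grade, platelet and distant metastasis, and it includes transfusion during hospitalization. Membership of the list therefore says nothing about timing. Its place beside 30-day mortality in item 1 is weak evidence as well, since it stands just as close to BCLC stage. If use was already ongoing at time zero, it is a legitimate baseline covariate, and dropping it could remove a confounder. The definition might also be in the protocol, which is not at hand.

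A reader might further infer that the surgery HR is certainly biased, or that a null drug would show an HR near 0.4. The documents support neither. The first needs both a late start and a difference in use or timing between groups, and the SAP gives no use by group, so even the direction is unknown. The second arises only under the very late starts of step 3.

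What stands is that the handling itself is written in the SAP. Both items specify methods for fixed groups and place no limit on when sorafenib was begun. A later start is plausible for a drug therapy listed separately from treatment, and the plan as worded would count such use as a baseline factor.

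**Conclusion.** The concern holds in conditional form. If sorafenib starts after OS time zero, its own HR in items 2 and 4 is biased towards benefit: about 0.57 to 0.92 for a null drug begun by a subset at a median of 1 to 6 months, and about 0.4 if all survivors remain at risk of a late start. The surgery HR is then near its true value with equal use. It shifts by up to about 18% with 50/10% or 10/50% intended use, and by about 20 to 30% in most of the unequal scenarios of step 3 (36% in the most unequal). Its direction follows which group uses more. If sorafenib starts at time zero, there is no bias.

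These sizes rest on exponential survival, a non-surgical median OS of 6 to 8 months, 60 months of follow-up and a drug with no effect. They are illustrations, not estimates for this study. The change from a total to a conditional surgery effect, which applies if the drug works, was reasoned and not simulated.

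**What to change.** - **Items 2 and 4:** take sorafenib started after time zero out of the univariate list and out of the Cox model that yields the surgery conclusion. Keep only use already ongoing at time zero as a fixed baseline covariate, and state what time zero is.
- **Item 1:** report later sorafenib use as treatment received, apart from the baseline characteristics.
- **If its association with OS is wanted:** fit a separate secondary Cox model with sorafenib as a time-dependent covariate, unexposed until the start date (SPSS Cox allows this), or use a landmark analysis. Do not read the surgery effect from it.

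The cost is a change of wording and re-run models. Start dates must also be taken from the charts, both to separate baseline from later use and to run the secondary model.
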